2.1.1 General definitions

Investigational drug and study treatment

Investigational drug, study treatment and *study drug* will refer to the pazopanib only.

Study treatment will be used throughout this document.

Date of first administration of study treatment

The date of first administration of study treatment is defined as the first date when a non-zero dose of study treatment is administered and recorded on the Dosage Administration Record (DAR) eCRF. The date of first administration of study treatment will also be referred as *start of study treatment*.

Date of last administration of study treatment

The date of last administration of study treatment is defined as the last date when a non-zero dose of study treatment is administered and recorded on DAR eCRF. The date of last administration of study treatment will also be referred to as end of study treatment.

Study day

The study day, describes the day of the event or assessment date, relative to the reference start date.

The study day is defined as:

- The date of the event (visit date, onset date of an event, assessment date etc.) – reference start date + 1 if event is on or after the reference start date;
- The date of the event (visit date, onset date of an event, assessment date etc.) – reference start date if event precedes the reference start date.

The reference date for all assessments (safety, efficacy, QoL/PRO, etc.) is the start of study treatment.

The study day will be displayed in the data listings. If an event starts before the reference start date, the study day displayed on the listing will be negative.

Time unit

A year length is defined as 365.25 days. A month length is 30.4375 days (365.25/12). If duration is reported in months, duration in days will be divided by 30.4375. If duration is reported in years, duration in days will be divided by 365.25.

The cycle length is 28 days from day 1 to day 28.

Baseline

For safety and efficacy evaluations, the last available assessment on or before the date of start of study treatment is defined as “baseline” assessment.

If patients have no value as defined above, the baseline result will be missing.

On-treatment assessment/event and observation periods

For adverse event reporting the overall observation period will be divided into three mutually exclusive segments:

1. *pre-treatment period*: from day of patient's informed consent to the day before first administration of study treatment

2. **on-treatment period:** from date of first administration of study treatment to 30 days after date of last actual administration of any study treatment (including start and stop date)
3. **post-treatment period:** starting at day 30+1 after last administration of study treatment.

Safety summaries (tables, figures) include only data from the on-treatment period with the exception of baseline data which will also be summarized where appropriate (e.g. change from baseline summaries). In addition, a separate summary for death including on-treatment and post-treatment deaths will be provided. In particular, summary tables for adverse events (AEs) will summarize only on-treatment events, with a start date during the on-treatment period (**treatment-emergent** AEs).

However, all safety data (including those from the post-treatment period) will be listed and those collected during the pre-treatment and post-treatment period will be flagged.

Windows for multiple assessments of PRO

In order to summarize PRO measures and performance status (PS) collected over time (including unscheduled visits), the assessments will be time slotted. The following general rule will be applied in creating the assessment windows: If more than one assessment is done within the same time window, the assessment performed closest to the target date will be used. If two assessments within a time window are equidistant from the target date, then the worst of the two assessments will be used. If multiple assessments on the same date then the worst case will be used. Data obtained at the end of treatment will be classified as other assessment in the corresponding time window. Data from all assessments (scheduled and unscheduled), including multiple assessments, will be listed.

Note that only data collected under treatment (i.e. while the patient is treated) will be included in the time to definitive deterioration. The end of treatment assessment will be included if collected within 30 days of the last dose intake.

Table 2-1 Time windows for EQ-5D-5L, KPS and FKSI-DRS assessments

Assessment	Target day of	Time Interval
Baseline		≤ Day 1
Cycle 2 Day 1	29	Day 2 to day 42
Cycle 3 Day 1	57	Day 43 to day 70
Cycle 4 Day 1	85	Day 71 to day 98
Cycle 5 Day 1	113	Day 99 to day 126
Cycle 6 Day 1	141	Day 127 to day 154
Cycle 7 Day 1	169	Day 155 to day 196
Cycle 9 Day 1	225	Day 197 to day 252
Cycle 11 Day 1	281	Day 253 to day 308
Cycle 13 Day 1	337	Day 309 to day 378
Cycle 16 Day 1	421	Day 379 to day 462

Every 3 rd cycle until EOT Cycle k Day 1 (k≥19) End of Treatment	d=(k-1)*28+1	Day d-42 to day d+41 Assessment taken at the end of treatment visit Note: EOT data visit are included if obtained within 30 days of last non-0 dose intake.
<hr/> 
Study Day 1 = start date of study treatment Post treatment study day 1=end of treatment date + 1 day 30 days is considered to be the time until total drug elimination
 <hr/>		

Last contact date

The last contact date will be derived for patients not known to have died at the analysis cut-off using the last complete date among the following:

Table 2-1 Last contact date data sources

Source data	Conditions
Start date of study treatment	No condition
Last contact date/last date patient was known to be alive from 'Survival Information' page	Patient status is reported to be alive.
Start/End dates from further antineoplastic therapy	Non-missing medication/procedure term.
Start/End dates from drug administration record	Non-missing dose. Doses of 0 are allowed.
End of treatment date from end of treatment page	No condition.
Tumor (RECIST) assessment date	Evaluation is marked as 'done'.
Laboratory collection dates	Sample collection marked as 'done'.
Vital signs date	At least one non-missing parameter value
Performance Status date	Non-missing performance status
Start/End dates of AE	Non-missing verbatim term

The last contact date is defined as the latest complete date from the above list on or before the data cut-off date. The cut-off date will not be used for last contact date, unless the patient was seen or contacted on that date. No date post cut-off date will be used. Completely imputed dates (e.g. the analysis cut-off date programmatically imputed to replace the missing end date of a dose administration record) will not be used to derive the last contact date. Partial date imputation is allowed only for event (death)/censoring if coming from 'Survival information' eCRF.

The last contact date will be used for censoring of patients in the analysis of overall survival.

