7.1.5.3 Survival follow-up

In order to assess overall survival, patients will be followed for survival every 12 weeks until the study ends (i.e., LPFV + 2 years). Patients, who discontinue study treatment without disease progression by RECIST 1.1 and enter the efficacy follow-up, will not begin the survival follow-up until after the efficacy follow-up period ends. Patients, who discontinue study treatment due to progression by RECIST 1.1 at any time or for any reason after LPFV + 1 year, will begin survival follow-up following end of treatment. Survival information can be obtained by clinical visits or telephone calls until death, lost to follow up, the patients withdraws consent for survival follow-up or the study ends. In addition to this survival follow-up, the first antineoplastic therapy to be administered to the patient since study drug discontinuation will be documented on the “Antineoplastic Therapy Since Discontinuation of Study Treatment” eCRF pages.

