10.5.2 Other secondary efficacy objectives

Overall response rate (ORR)

ORR is defined as the proportion of patients with best overall response (BOR) of CR or PR based on local investigator's assessment according to RECIST 1.1 (see [Appendix 2](#) for details). Determination of BOR of PR or CR will be based on confirmed PR/CR as per RECIST 1.1.

ORR will be calculated based on the FAS and its exact 95% confidence interval ([Clopper and Pearson 1934](#)) will be presented.

Clinical benefit rate (CBR)

CBR is defined as the proportion of patients with a best overall response of confirmed CR, or PR or an overall lesion response of SD or Non-CR/Non-PD lasting ≥ 24 weeks based on local investigator's assessment according to RECIST 1.1.

CBR and its exact 95% confidence interval will be provided using FAS population.

Overall survival (OS)

OS is defined as the time from date of start of pazopanib treatment to date of death due to any cause. If a patient is not known to have died, then OS will be censored at the latest date the patient was known to be alive (on or before the cut-off date).

OS will be analyzed in the FAS population. The OS distribution will be estimated using the Kaplan-Meier method. The Kaplan-Meier curve will be graphically presented, and the median, 25th and 75th percentiles will be shown along with the corresponding 95% confidence intervals. OS probability at selected time-points (e.g., 6, 12 and 24 months) will also be estimated.

Duration of response (DOR)

DOR only applies to patients, whose best overall response is confirmed CR or PR, as per local investigator's assessment, according to RECIST 1.1. DOR is defined as the time from the date of first documented response of CR or PR (i.e., the start date of response, not the date when response was confirmed), to the date of the first documented progression or death due to underlying cancer, whichever comes first. In patients continuing without progression or death due to underlying cancer DOR will be censored at the date of their last adequate tumor assessment. DOR will be estimated using the Kaplan-Meier method. The median, 25th and 75th percentiles, and the corresponding 95% confidence intervals will be provided.

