2.1 Data analysis general information

The primary and final analyses will be performed by Novartis and/or a designated CRO. SAS version 9.4 or later software will be used to perform all data analyses and to generate tables, figures and listings.

Data included in the analysis

The cut-off date for the primary analysis of study data will be established after all enrolled patients have completed 6 cycles of treatment or have discontinued study. The final analysis cut-off date will be established 2 years after the last patient has started treatment. All statistical analyses will be performed using all data collected in the database up to the data cut-off date. All data with an assessment date or event start date (e.g. vital sign assessment date or start date of an adverse event) prior to or on the cut-off date will be included in the analysis. Any data collected beyond the cut-off date will not be included in the analysis and will not be used for any derivations.

All events with start date before or on the cut-off date and end date after the cut-off date will be reported as 'ongoing'. The same rule will be applied to events starting before or on the cut-off date and not having documented end date. This approach applies, in particular, to adverse event and concomitant medication reports. For these events, the end date will not be imputed and therefore will not appear in the listings.

General analysis conventions

Pooling of centers: Unless specified otherwise, data from all study centers will be pooled for the analysis. Due to expected small number of patients enrolled at centers, no center effect will be assessed.

Qualitative data (e.g., gender, race, etc.) will be summarized by means of contingency tables; a missing category will be included as applicable. Percentages will be calculated using the number of patients in the relevant population or subgroup as the denominator.

Quantitative data (e.g., age, body weight, etc.) will be summarized by appropriate descriptive statistics (i.e. mean, standard deviation, median, minimum, and maximum and in addition when specified 25th and 75th percentiles).

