2.7.1 Secondary endpoints

Overall Survival (OS)

Overall Survival (OS) is defined as the time from date of start of treatment to date of death due to any cause. A cut-off date will be established for each analysis of OS. All deaths occurring on or before the cut-off date in the FAS will be used in the OS analysis.

If a patient is not known to have died at the time of analysis cut-off, OS will be censored at the date of last contact.

The OS analyses will also be provided by the line of therapy subgroups defined in [Section 2.2.1](#).

Overall Response Rate (ORR)

ORR is defined as the proportion of patients with best overall response (BOR) of complete response (CR) or partial response (PR) according to RECIST 1.1 (see [Appendix 2](#) of the study protocol). ORR will be calculated based on the FAS using local investigators review of tumor assessment data. Tumor assessments performed before the start of any further antineoplastic therapy (i.e. any additional secondary antineoplastic therapy or surgery) will be considered in

the assessment of BOR. Palliative radiotherapy is not allowed as per protocol and those will be considered as anti-neoplastic therapy usage.

The ORR analyses will also be provided by the line of therapy subgroups defined in [Section 2.2.1](#).

Clinical benefit rate (CBR)

CBR is defined as the proportion of patients with a best overall response (BOR) of confirmed CR or PR, or SD or Non-CR/Non-PD lasting 24 weeks or longer, according to RECIST v1.1 criteria. A patient will be considered to have SD for 24 weeks or longer if a SD response is recorded at (24 -1) weeks or later from start of study treatment, allowing for the ± 1 week visit window for tumor assessments. CBR will be calculated using the FAS based on the investigators' tumor assessments.

Duration of response (DOR)

DOR only applies to patients whose best overall response is complete response (CR) or partial response (PR) according to RECIST v1.1 based on local investigators review of tumor assessment data. The start date is the date of first documented response of CR or PR (i.e., the start date of response, not the date when response was confirmed), and the end date is defined as the date of the first documented progression or death due to underlying cancer. Patients continuing without progression or death due to underlying cancer will be censored at the date of their last adequate tumor assessment using the censoring rule described for PFS analysis.

Time to response

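### At the primary analysis, OS counts deaths up to the cut-off but censors survivors at an earlier contact, which biases the curve modestly downward

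*SAP*

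**What the plan says.** **Deaths.** SAP 2.7.1: "All deaths occurring on or before the cut-off date in the FAS will be used in the OS analysis".

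**Survivors.** SAP 2.7.1: "If a patient is not known to have died at the time of analysis cut-off, OS will be censored at the date of last contact". SAP 2.1.1 defines that date as the latest complete date from a list of sources, on or before the cut-off. It adds "The cut-off date will not be used for last contact date, unless the patient was seen or contacted on that date" and "No date post cut-off date will be used". Protocol 10.5.2 similarly censors at the latest date the patient was known alive, no later than the cut-off.

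**Contacts.** Protocol 7.1.5.3: "patients will be followed for survival every 12 weeks until the study ends". Telephone contact is allowed. Neither document ties a contact to an analysis cut-off.

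**General data rule.** SAP 2.1 includes data by event or assessment date up to the cut-off, but also says "Any data collected beyond the cut-off date will not be included in the analysis and will not be used for any derivations". It does not say what happens to a death that is dated before the cut-off and learned of afterwards.

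**Outputs.** SAP 2.7.2 plans Kaplan-Meier quartiles and survival at 6, 12 and 24 months. SAP 2.7.1 adds OS by line of therapy and sets a cut-off for each OS analysis.

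**The concern.** Take two patients in survival follow-up, each last contacted 6 weeks before the cut-off and next contacted 6 weeks after it. The second call shows that one died 2 weeks before the cut-off. Under SAP 2.7.1 that death is an event. The other is alive at the second call, and so was alive at the cut-off. Under SAP 2.1.1 that patient is censored 6 weeks before the cut-off. The same kind of call is used when it reports a death and discarded when it reports survival.

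Kaplan-Meier estimation assumes that censoring carries no information about the outcome. Here, over the stretch between last contact and cut-off, deaths stay in and survivors leave the risk set. The estimate is pulled down, most in the later part of the curve.

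There is no control arm in which the same bias would arise and cancel. Protocol 2.2 says the results will be viewed in light of previously reported data.

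**Working it through.** **1. Reproduce the plan's frame.** The documents give no figure for OS precision or bias, so the check starts from Protocol Table 10-1 (PFS). Inputs from Protocol 10.8: accrual A = 12 months, follow-up F = 6 months after LPFV, N = 100, median 5 months. With exponential times and λ = ln 2 / median:

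- Events d = N × [1 − (e^(−λF) − e^(−λ(A+F))) / (Aλ)] = 100 × [1 − (0.4353 − 0.0825) / 1.6636] = 78.8
- 95% CI = 5 × exp(±1.96 / √78.8) = 4.01 to 6.24

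This matches the table. The other eight rows also match, as does the 4.77 to 7.55 interval in Protocol 2.2 (median 6, N = 100, d = 72.95).

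**2. Simulate OS on that frame.** 400,000 patients per scenario were simulated with exponential OS. Two inputs are assumptions, because the documents give neither for this population: the OS median, and a median of 5 months to treatment discontinuation. Visits on treatment follow the protocol schedule, then an end-of-treatment visit, a 30-day safety contact and 12-weekly contacts. The 8-weekly efficacy follow-up contacts are not modelled.

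Survivors are censored on average 5.2 to 5.3 weeks before the cut-off, with a maximum of 12.0 weeks.

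**3. 12-month OS at the primary analysis.** The third column counts all deaths up to the cut-off, as SAP 2.7.1 says. The fourth drops deaths first learned of after it, the strict reading of SAP 2.1. Differences from the second column, in points, are in brackets.

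| True median (months) | Survivors censored at cut-off | SAP rule, all deaths | SAP rule, late-learned deaths dropped |
|---|---|---|---|
| 12 | 50.0% | 47.2% (−2.8) | 49.4% (−0.6) |
| 18 | 63.0% | 60.6% (−2.4) | 62.5% (−0.6) |
| 24 | 70.7% | 68.7% (−2.1) | 70.2% (−0.5) |

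(Differences use unrounded values.) Censoring survivors at the cut-off recovers the true curve.

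- At 6 months the bias is only 0.1 to 0.3 points. The shortest potential follow-up is about 6 months and the longest gap is 84 / 30.4375 = 2.8 months, so survivors start to be removed only at about 3.2 months.
- At a true median of 12 months, the Kaplan-Meier median is 11.2 against 12.0, and 0.8 / 12.0 = 7% low.
- In the tail the gap grows. At 16 months it is 32.8% against 39.8% (true median 12) and 47.3% against 54.0% (true median 18).

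A separate run with the cut-off 24 weeks after the last start gave similar results: 46.5% against 49.6% at a true median of 12 months, and 60% against 63% at 18.

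**4. Sensitivity of the 12-month bias.**

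- Half of the deaths in the gap learned: roughly halved.
- 24-month accrual (an assumption), all deaths known: 48.8% against 50.0% (−1.2) at a true median of 12 months, and 61.8% against 62.9% (−1.1) at 18.
- Sampling SD of 12-month OS at N = 100: 5.8, 5.4 and 5.1 points for true medians of 12, 18 and 24 months.

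**5. Final analysis (24 months after LPFV).** Survivors start to be removed only at about 24 − 2.8 = 21.2 months. OS at 6, 12 and 16 months is unchanged, and 24-month OS moves by about 0.2 points. The median moves from 24.06 to 23.95 months at a true median of 24, and from 28.03 to 27.41 (2%) at 28.

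**The case against.** The strongest objection is that the plan may not count late-learned deaths at all. SAP 2.1 bars data collected after the cut-off from any derivation, and the opening of Protocol section 10 speaks of data captured up to the cut-off. On that reading a late report of death falls out just as a late report of survival does, and the 12-month bias is well under 1 point. This stands as a limit on size. It does not remove the point, because SAP 2.1 also includes data by event date and SAP 2.7.1 says that all such deaths count. The result therefore depends on which sentence the programmer follows.

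The contact gap is also smaller than 12 weeks suggests. Twelve weeks is the maximum; the average is about 5. SAP 2.1.1 also draws on adverse-event, dosing and further-therapy dates, which can fall between visits and were not modelled. With 30% of off-treatment patients assumed to be on 8-weekly contacts, the mean lag is 4.9 weeks.

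Materiality is limited as well. OS is descriptive and secondary, Protocol 2.2 disclaims any comparison with a standard of care, the bias is smaller than the sampling error at 12 months, and the final analysis supersedes the primary one. All of this stands. Still, a confidence interval conveys sampling error and does not convey a bias in one direction.

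A reader might go further and infer that the primary report would give a finite median of about 15 months where the right answer is that the median is not reached. The large simulation does show 15.3 months at a true median of 18. The documents do not support this as an expected result. They give no OS assumption, and 18 months is the limit of follow-up on the planned frame. At N = 100, on the same assumptions, the median is reached in 37% of trials even with survivors censored at the cut-off, against 69% under the SAP rule. With 24-month accrual the contrast is 17.0 against 18.0 months. Nor are 15 or 16 months planned landmarks, and 24 months lies beyond follow-up at the primary cut-off.

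**Conclusion.** The point holds in a limited form. As written, SAP 2.7.1 and 2.1.1 treat deaths and survivors differently over the weeks before the cut-off, and the primary-analysis OS curve is biased downward.

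The figure of 2 to 3 points at 12 months, with the median about 7% low at a true median of 12 months, is an upper scenario. It rests on the planned 12-month accrual, a cut-off about 6 months after LPFV, assumed exponential OS with medians of 12 to 24 months, an assumed median of 5 months on treatment, and every death up to the cut-off being known. Slower accrual, incomplete capture of late deaths or the strict reading of SAP 2.1 brings the 12-month bias to roughly 1 point or less. No test, alpha or power is affected. The correction is worth making because it is cheap and the two SAP sections need reconciling in any case.

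**What to change.** 1. In SAP 2.1.1, state that for OS a patient documented alive on any date after the cut-off is censored at the cut-off date. Keep the last-contact rule for patients without such a contact.
2. Reconcile SAP 2.1 with SAP 2.7.1 so that one ascertainment rule covers both outcomes. State that vital status learned after the cut-off but before database lock is used for OS, whether it is a death dated on or before the cut-off or proof of survival past it. Without this exception, the bar in SAP 2.1 would block the first change. Align the wording of Protocol 10.5.2 at the next opportunity.
3. Optionally, add a telephone survival check at each cut-off to Protocol 7.1.5.3. Routine 12-weekly contacts made before database lock can supply most of the information without it.

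The cost is a minor programming change and a narrow exception to the cut-off rule, confined to OS censoring. The optional check adds one call per surviving patient at each cut-off.
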